**Figure RHBV.2. Illustration of graphical multiple testing procedure.**

There will be no adjustment for multiple comparisons for any other analyses.

### **9.3. Treatment Group Comparability**

#### **9.3.1. Patient Disposition**

All patients who prematurely discontinue from the study treatment and/or from the study will be identified, and the extent of their participation in the study will be reported.

Patient disposition will be summarized for each treatment period with reasons for discontinuation. The reasons for discontinuation during Period 2 will be compared between treatment groups using Fisher's exact test.

#### **9.3.2. Patient Characteristics**

Patient characteristics and baseline clinical measures will be summarized for each treatment period. Baseline characteristics will include sex, age, age category, weight, body mass index (BMI), race, geographic region, country, baseline disease activity (BASDAI), duration of disease, HLA-B27 positivity, baseline CRP (% of nonelevated or elevated), baseline MRI status, and history of extra-axial disease manifestations. Baseline clinical measurements may include ASDAS, CRP, BASFI, BASMI, chest expansion, Fatigue NRS, Patient Global NRS, total back pain, spinal pain at night due to AS, spinal pain due to AS, inflammation (mean of questions 5 and 6 of BASDAI), MASES, SPARCC Enthesitis, TJC, and SJC.

Treatment group comparisons in Period 2 will be conducted using Fisher's exact test for categorical data and an analysis of variance (ANOVA) with treatment as a factor for continuous data.

#### **9.3.3. Concomitant Therapy**

Previous and concomitant medications will be summarized for patients who enter each treatment period and will be presented by WHO Anatomic Therapeutic Class Level 4 and WHO preferred term. Concomitant DMARDs, concomitant oral corticosteroids, and concomitant NSAIDs will also be summarized. Treatment group comparisons in Period 2 will be conducted using Fisher's exact test.

#### **9.3.4. Treatment Compliance**

Treatment compliance with investigational product will be summarized for patients who enter each treatment period. A patient will be considered overall compliant for each study period if he/she is missing no more than 20% of the expected doses, does not miss 2 consecutive doses and does not over-dose (that is, take more injections at the same time point than specified in the protocol).

Proportions of patients compliant by visit and overall will be compared between treatment groups during Period 2 using Fisher's exact test.

## 9.4. Primary and Secondary Analyses

### 9.4.1. Primary Analyses

The primary analysis, the proportion of patients with ASAS40 at Week 16 compared with placebo, will be based on the ITT Population. In addition, an analysis of the PPS Population will be used to support the primary efficacy analysis.

Treatment comparisons between each ixekizumab treatment group and placebo in the proportion of patients achieving an ASAS40 response at Week 16 (Visit 8) will be analyzed using the logistic regression model defined in Section 9.2.1. Missing data will be imputed using the NRI method described in Section 9.2.5.

Secondary analyses for ASAS40 at Week 16 will be conducted using categorical MMRM and Fisher's exact test as described in Section 9.2.1.

### 9.4.2. Secondary Analyses

#### 9.4.2.1. Major Secondary Analyses

The major secondary analyses at Week 16 will be based on the ITT population for Period 2. The major secondary comparisons will be based on the multiple testing procedure detailed in Section 9.2.6. Treatment comparisons in the proportion of patients achieving a categorical response at Week 16 (Visit 8) will be analyzed using the logistic regression model defined in Section 9.2.1. For categorical responses, missing data will be imputed using the NRI method described in Section 9.2.5. Treatment comparisons in the continuous measures will be analyzed using the MMRM model defined in Section 9.2.1.

Table RHBV.5 summarizes the primary and major secondary outcomes and analysis methods. All analyses listed will be performed based on the ITT Population unless otherwise specified.

**Table RHBV.5. Primary and Major Secondary Outcome Analyses**

Outcome Measure	Primary Analysis Method	Secondary Analysis Method
ASAS40 (primary efficacy outcome)	Logistic regression analysis with NRI	Categorical MMRM Fisher's exact test with NRI Logistic regression analysis with NRI on PPS
ASAS20 (major secondary outcome)	Logistic regression analysis with NRI	Categorical MMRM Fisher's exact test with NRI Logistic regression analysis with NRI on PPS
Change from baseline in ASDAS (major secondary outcome)	MMRM	ANCOVA with mBOCF/LOCF
BASDAI50 (major secondary outcome)	Logistic regression analysis with NRI	Categorical MMRM Fisher's exact test with NRI
Change from baseline in BASFI (major secondary outcome)	MMRM	ANCOVA with mBOCF/LOCF
ASDAS inactive disease (major secondary outcome)	Logistic regression analysis with NRI	Categorical MMRM Fisher's exact test with NRI
Change from baseline in MRI of spine [SPARCC score] (major secondary outcome)	ANCOVA with observed case analysis a	Secondary analysis maybe specified in SAP
Change from baseline in SF-36 PCS (major secondary outcome)	MMRM	ANCOVA with mBOCF/LOCF
Change from baseline in the ASAS-HI (major secondary outcome)	MMRM	ANCOVA with mBOCF/LOCF

Abbreviations: ANCOVA = analysis of covariance; ASAS = Assessment of Spondyloarthritis International Society; ASAS HI = Assessment of Spondyloarthritis International Society Health Index; ASDAS = Ankylosing Spondylitis Disease Activity Score; BASDAI50 = Bath Ankylosing Spondylitis Disease Activity Index 50; BASFI = Bath Ankylosing Spondylitis Functional Index; LOCF = last observation carried forward; mBOCF = modified baseline observation carried forward; MMRM = mixed-effects model of repeated measures; MRI = magnetic resonance imaging; NRI = nonresponder imputation; PPS = per-protocol set; SAP = statistical analysis plan; SF-36 PCS = Short Form-36 physical component scores; SPARCC = Spondyloarthritis Research Consortium of Canada.

a Only patients with both baseline and Week 16 MRI scores will be included in the observed case analysis.

#### **9.4.2.2. Other Secondary Efficacy Analyses**

There will be no adjustment for multiple comparisons. Analyses will be conducted for the other secondary efficacy objectives defined in Section 3. Specific details of analyses will be specified in the SAP.

##### **9.4.2.2.1. Period 2 (Blinded Treatment Dosing Period)**

Unless otherwise specified, the other secondary analyses during Period 2 will be based on the ITT Population.

Treatment comparisons in the proportion of patients achieving a categorical response at specified time points will be analyzed using the logistic regression model defined in Section 9.2.1.

Missing data will be imputed using the NRI method described in Section 9.2.5.

For all continuous efficacy variables that are collected at repeated visits, treatment group comparisons will be analyzed using the MMRM model defined in Section 9.2.1. No imputation methods are applied to MMRM analysis. Additional analyses will be conducted using the ANCOVA model defined in Section 9.2.1; missing data will be imputed by the mBOCF method as described in Section 9.2.5. For continuous efficacy variables that are collected only once within Period 2, analyses will be made using the ANCOVA model with the mBOCF method.

#### **9.4.2.2.2. Period 3 (Extended Treatment Period)**

Data collected in this study period will be summarized for the Extended Treatment Period Population. The within-treatment group comparisons may be conducted as appropriate.

#### **9.4.3. Other Exploratory Analyses**

Details about exploratory analyses will be included in the SAP or appropriate biomarker analysis plan.

### **9.5. Safety Analyses**

Safety will be assessed by summarizing and analyzing AEs including adjudicated cerebrocardiovascular events, laboratory analytes including neutrophil counts, QIDS-SR16, C-SSRS, and vital signs. The duration of treatment exposure will also be summarized

For Period 2 (Blinded Treatment Dosing Period), safety data will be summarized for the Safety Population. Treatment group comparisons will be performed on categorical safety data using Fisher's exact test as described in Section 9.2.1; continuous safety data will be analyzed by an ANCOVA model.

For Period 3 (Extended Treatment Period), the safety data will be summarized and no treatment group comparisons will be performed.

For Period 4 (Post-Treatment Follow-Up Period), safety data will be summarized according to the treatment patients were on prior to entering Period 4.

The categorical safety measures will be summarized with incidence rates. The mean change of the continuous safety measures will be summarized by visits.

Further details will be described in the SAP.

#### **9.5.1. Adverse Events**

Adverse events are classified based upon the Medical Dictionary for Regulatory Activities (MedDRA). A treatment-emergent adverse event (TEAE) is defined as an event that first occurred or worsened in severity after baseline and on or prior to the date of the last visit within the treatment period. Both the date/time of the event onset and the date/time of the first study drug injection are considered when determining TEAEs. Treatment-emergent adverse events will be assigned to the treatment period in which they first occurred or worsened. A follow-up emergent adverse event (FEAE) is defined as an event that first occurred or worsened in severity after the date of Week 52 (Visit 15) or the ETV. For events that are gender specific, the denominator and computation of the percentage will include only patients from the given gender.

An overall summary of AEs will be provided for each of the treatment periods, including the number and percentage of patients who experienced TEAEs, TEAEs by maximum severity, deaths, SAEs, TEAEs related to study drug, discontinuations from the treatment due to an AE, and treatment-emergent AESIs. Treatment-emergent adverse events (all, by maximum severity, and TEAEs possibly related to study drug by the investigator), SAEs including deaths, and AEs that lead to treatment discontinuation will be summarized and analyzed by MedDRA system organ class (SOC) and preferred term.

In addition to general safety parameters, safety information on specific topics of AESIs will also be presented. Potential AESIs will be identified by a standardized MedDRA query (SMQ) or a Lilly defined MedDRA preferred term listing.

Follow-up emergent adverse events, SAEs including deaths, and AEs that lead to study discontinuation will be summarized for Period 4.

### **9.5.2. Clinical Laboratory Tests**

Laboratory assessments will be presented as mean changes from baseline, and as incidence of treatment-emergent abnormal, high, or low laboratory values (see below). Shift tables will be presented for selected parameters.

- For categorical lab tests:
  - Treatment-emergent **abnormal** value = a change from normal at all baseline visits to abnormal at any time postbaseline.
- For continuous lab tests:
  - Treatment-emergent **high** value = a change from a value less than or equal to the high limit at all baseline visits to a value greater than the high limit at any time postbaseline.
  - Treatment-emergent **low** value = a change from a value greater than or equal to the low limit at all baseline visits to a value less than the low limit at any time postbaseline.

### **9.5.3. Vital Signs, Physical Findings, and Other Safety Evaluations**

Vital signs will be presented as mean changes from baseline and as incidence of treatment-emergent high or low values (see below) and will be summarized both pre- and postdose at Week 0 (Visit 2), Week 16 (Visit 8) and Week 20 (Visit 9) as applicable.

- For treatment-emergent high and low:

- A treatment-emergent high result is defined as a change from a value less than or equal to the high limit at baseline to a value greater than the high limit at any time that meets the specified change criteria during the treatment period.
- A treatment-emergent low result is defined as a change from a value greater than or equal to the low limit at baseline to a value less than the low limit at any time that meets the specified change criteria during the treatment period.

The maximum postbaseline QIDS-SR16 total score will be summarized by treatment group, and a shift table will be produced for the change from baseline in QIDS-SR16 total score category.

Suicide-related thoughts and behaviors and self-injurious behavior with no suicidal intent, based on the C-SSRS, will be listed by patient.

## 9.6. Pharmacokinetic/Pharmacodynamic/Immunogenicity Analyses

Observed ixekizumab serum concentrations will be summarized by treatment regimen, visits and corresponding time when sampling occurred.

As appropriate, the PK and the exposure-response relationship between ixekizumab exposure and clinically important efficacy measures (for example, ASAS40 or ASAS20) may be explored using graphical methods and/or a modeling approach. Pharmacokinetic and/or exposure-response data from this study may be combined with existing PK and/or exposure-response data from other studies, if considered appropriate.

If a trend or statistically significant difference between the ixekizumab dose cohorts and/or the placebo cohort is noted in any safety endpoint, the exposure relationship for this endpoint may be explored graphically.

In addition, the potential impact of immunogenicity on ixekizumab exposure and/or efficacy responses may be evaluated by graphical assessments, as appropriate, to compare drug exposure or efficacy responses between ADA negative and ADA positive patients at corresponding visits, or before and after ADA development for patients who develop ADA. Both treatment-emergent only and all ADA positive/negative patients may be explored. A similar approach may be taken if patients become NAb positive. The effect of immunogenicity may be evaluated as a covariate in the population PK and exposure-response analyses, if applicable.

## 9.7. Other Analyses

### 9.7.1. Health Economics

There will be no adjustment for multiple comparisons. Analyses will be conducted for the other secondary health outcomes objectives as defined in Section 3.

#### Period 2 (Blinded Treatment Dosing Period):

Unless otherwise specified, the other secondary analyses during Period 2 will be based on the ITT population.

Treatment comparisons in the proportion of patients achieving a categorical response at specified time points will be analyzed using the logistic regression model defined in Section 9.2.1. Missing data will be imputed using the NRI method described in Section 9.2.5.

For all continuous health outcomes variables that are collected at repeated visits, treatment group comparisons will be analyzed using the MMRM model defined in Section 9.2.1. No imputation methods are applied to MMRM analysis. Additional analyses will be conducted using the ANCOVA model defined in Section 9.2.1; missing data will be imputed by the mBOCF method as described in Section 9.2.5. For continuous health outcomes variables that are collected only once within the Period 2, analyses will be made using the ANCOVA model with the mBOCF method.

### **Period 3 (Extended Treatment Period):**

Data collected in Period 3 will be summarized for the Extended Treatment Period Population. The within-treatment group comparisons may be conducted as appropriate.

Additional analyses of health outcomes measures will be specified in the SAP.

### **9.7.2. Subgroup Analyses**

Subgroup analyses will be conducted for ASAS40 and selective major secondary outcomes (defined in the SAP) at Week 16 (Visit 8) using the ITT Population.

Subgroup analyses may be conducted based on gender, age category, race, baseline disease severity, country, geographic region, baseline CRP status, baseline MRI status, presence of HLA-B27.

For ASAS40, a logistic regression model with treatment, subgroup, and the interaction of subgroup-by-treatment included as factors will be used. The subgroup-by-treatment interaction will be tested at the significance level of 0.10. Treatment group differences will be evaluated within each category of the subgroup using Fisher's exact test, regardless of whether the interaction is statistically significant. Missing data will be imputed using NRI as described in Section 9.2.5. If any group within the subgroup is <10% of the total population, only summaries of the efficacy data will be provided (that is, no inferential testing).

For continuous efficacy outcome (for example, mean change from baseline in ASDAS), an ANCOVA model with treatment, baseline value, subgroup, and the interaction of subgroup-by-treatment will be used. The subgroup-by-treatment interaction will be tested at the significance level of 0.10. Treatment group differences will be evaluated within each category of the subgroup using an ANCOVA model with treatment and baseline value as a covariate, regardless of whether the interaction is statistically significant. Missing data will be imputed using the mBOCF method as described in Section 9.2.5.

Detailed description of the subgroup variables will be provided in the SAP. Additional subgroup analyses on efficacy or subgroup analyses on safety may be performed as deemed appropriate and necessary.

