## 9. Statistical Considerations and Data Analysis

### 9.1. Determination of Sample Size

Approximately 320 patients will be randomized at a 1:1:1:1 ratio in the Blinded Treatment Dosing Period (Period 2) to ixekizumab 80 mg Q2W, ixekizumab 80 mg Q4W, adalimumab 40 mg Q2W, and placebo. With 80 patients per treatment group, this study will have approximately 96% power to test the superiority of ixekizumab Q2W to placebo for the ASAS40 at Week 16. The following assumptions were used for the power calculations for ASAS40 response rates at Week 16 regardless of starting dose: 44% for ixekizumab 80mg Q2W treatment group and 16% for the placebo group. A 2-sided Fisher's exact test at the 0.05 level is assumed. These assumptions are based on the review of historical clinical studies in rad-axSpA (etanercept, adalimumab, infliximab, certolizumab, and golimumab [Davis et al. 2003; van der Heijde et al. 2005 and 2006; Inman et al. 2008; Landewe et al. 2014]) and recent secukinumab data in patients who are TNF-naive (Baeten et al. 2014b; Sieper et al. 2014).

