#### 9.2.1. General Considerations for Analyses during the Blinded Treatment Dosing Period (Period 2)

Comparisons between each ixekizumab regimen (80 mg Q2W or 80 mg Q4W) and placebo, as well as comparisons between adalimumab and placebo, will be performed for all analyses in Period 2.

Period 2 starts at the first injection of study treatment at Week 0 (Visit 2) and ends prior to the first injection of study treatment at Week 16 (Visit 8) or the ETV (between Weeks 0 and 16).

Baseline will be defined as the last available value before the first injection for efficacy, health outcomes and safety analyses. In most cases, this will be the measure recorded at Week 0 (Visit 2). For efficacy measures, if the patient does not take any injection, the last available value on or prior to randomization date will be used. Change from baseline will be calculated as the visit value of interest minus the baseline value. For safety analyses using a baseline period, the baseline period is defined as the time from Visit 1 to the date/time of the first injection.

The randomization to treatment groups is stratified by country and baseline CRP status (nonelevated or elevated) as described in Section 6.2. The countries will be categorized into geographic regions for analysis. Geographic regions will be defined in SAP upon country finalization. Unless otherwise specified, the statistical analysis models will adjust for geographic region and baseline CRP status.

Unless otherwise specified, treatment groups of ixekizumab 80 mg Q2W and Q4W will be analyzed without regard to starting dose.

The primary analysis method for treatment comparisons of categorical efficacy, health outcomes variables at specific time points will be made using a logistic regression analysis with treatment, geographic region, and baseline CRP status in the model. The odds ratio and 95% confidence intervals (CIs) will be reported; treatment difference and 95% CIs will also be reported. Secondary analysis will be conducted using a Fisher's exact test.

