6.14. Subgroup Analyses

6.14.1. Efficacy Subgroup Analyses

Subgroup analysis will be conducted for the primary endpoints of proportion of patients achieving an ASAS40 response at Week 16 (NRI) using the ITT Population for the Period 2. The major secondary efficacy endpoints, the proportion of patients achieving ASAS20 (NRI) and ASDAS inactive disease (NRI) at Week 16, will also be conducted.

For categorical response variables (ASAS20, ASAS40, and ASDAS inactive disease), a logistic regression analysis with treatment, subgroup, and treatment-by-subgroup interaction as factors will be used. The treatment-by-subgroup interaction will be tested at the 10% significance level. Treatment group differences will be evaluated within each subgroup using the Fisher's exact test, regardless of whether the interaction is statistically significant. If any group within the subgroup (for example, yes, no) is <10% of the total population, only descriptive statistics will be provided for that subgroup (that is, no inferential testing).

Forest plots may be created to illustrate the treatment differences with 95% CIs between each of the ixekizumab treatment groups and placebo group, by each subgroup category.

The following subgroups will be analyzed:

- Patient Demographics Subgroups:
 - Sex
 - Age category: <40 years, ≥40 years
 - Age category: <50 years, ≥50 years
 - Age category: <65 years, ≥65 years
 - Weight: <70 kg, ≥70 kg
 - BMI: underweight (<18.5 kg/m²); normal (≥18.5 and <25 kg/m²); overweight (≥25 and <30 kg/m²); obese (≥30 and <40 kg/m²); or extreme obese (≥40 kg/m²)
 - Ethnicity: Hispanic/Latino, Non-Hispanic/Non-Latino
 - Race: American Indian/Alaska Native, Asian, Black/African American, Native Hawaiian or other Pacific Islander, White, or Multiple
- Geographic Region Subgroups:
 - Geographic region: Europe, non-Europe
 - Geographic region: America, Asia, Europe
 - Geographic region: North America (US including Puerto Rico if any, Canada), rest of the World
 - Geographic region: US (including Puerto Rico if any), non-US
- Baseline Severity of Disease Subgroups:
 - Baseline CRP categories:
 - ≤3.00 mg/L or >3.00 mg/L

- ≤ 5.00 mg/L or > 5.00 mg/L
 - ≤ 10.00 mg/L or > 10.00 mg/L
 - ≤ 15.00 mg/L or > 15.00 mg/L
- Baseline MRI status:
 - SPARCC SIJ score ≥ 2 or < 2
 - SPARCC Spine score ≥ 2 or < 2
 - ASSpiMRI-Berlin score > 0 or $= 0$
- Other Patient Characteristics Subgroups:
 - Duration of symptom since AxSpA onset category: < 10 years or ≥ 10 years;

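### The ASAS40 subgroup models leave out region and CRP status; adding them is a free gain of about 0 to 6 points of interaction power, and the within-level Fisher test is valid but conservative

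*Protocol*

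**What the plan says.** The Period 2 default in Protocol 9.2.1 is that "the statistical analysis models will adjust for geographic region and baseline CRP status". The sentence carries a proviso that lets a section specify otherwise, and SAP 6.1.1 repeats both the default and the proviso. The primary ASAS40 analysis follows the default.

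The subgroup sections depart from it. Protocol 9.7.2: "a logistic regression model with treatment, subgroup, and the interaction of subgroup-by-treatment included as factors will be used". SAP 6.14.1, for ASAS20, ASAS40 and ASDAS inactive disease: "a logistic regression analysis with treatment, subgroup, and treatment-by-subgroup interaction as factors will be used". The interaction is tested at 0.10. Protocol 9.7.2 then adds: "Treatment group differences will be evaluated within each category of the subgroup using Fisher's exact test". This is done whether or not the interaction is significant, and SAP 6.14.1 agrees. Levels holding under 10% of patients are only summarised.

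Randomisation is stratified by country and CRP status (Protocol 6.2), and countries are grouped into Europe and non-Europe for analysis (SAP 6.2). Elsewhere, for categorical efficacy, SAP 6.1.1 uses Fisher's test as a secondary method and as the fallback when the logistic model gives no result because data are sparse.

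**The concern.** Protocol 4.3 justifies stratifying on CRP because it has been reported to predict response to TNF inhibitors. The plan uses that information in the primary model and gives no reason for dropping it from the subgroup models. The same question can then be answered in two ways. SAP 6.4 tests treatment by region for the primary endpoint, which under the default would adjust for CRP. SAP 6.14.1 tests the same Europe/non-Europe interaction without CRP.

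These analyses inform the judgement of whether the ixekizumab effect is consistent across patients. Two losses are possible: a less sensitive interaction test, and within-level p-values that miss a real effect because of the test used. The two have different causes and should be sized separately.

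**Working it through.** **Inputs from the documents.** Protocol 9.1 gives the allocation ("Approximately 320 patients will be randomized at a 1:1:1:1 ratio"), the response rates ("44% for ixekizumab 80mg Q2W treatment group and 16% for the placebo group") and the test ("A 2-sided Fisher's exact test at the 0.05 level is assumed"). A level holding a share s of patients has about 80s per arm, so 10% is 8, 20% is 16, 50% is 40 and 80% is 64.

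**Assumptions, because the documents give no figure.** 60% elevated CRP; 50% Europe; odds ratios of 1 to 4 for CRP and 1 to 2 for region; strata either balanced or unbalanced between arms within a level; a two-sided 5% level for the within-level tests.

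**Step 1: the plan's own figure.** Power is the sum over all (x, y) of Bin(x; n, p1) × Bin(y; n, p2), counted where Fisher's two-sided p ≤ 0.05. With n = 80, p1 = 0.44 and p2 = 0.16 this is 96.7%. Protocol 9.1 states: "With 80 patients per treatment group, this study will have approximately 96% power". The figure reproduces.

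**Step 2: Fisher within a level.** Size uses the same sum with both rates at 16%. The comparators are:
- an unstratified score test, z = (p̂1 − p̂2) / √[p̄(1 − p̄) × 2/n];
- a Cochran-Mantel-Haenszel (CMH) score test over the four CRP-by-region strata, simulated with CRP odds ratio 2 and region odds ratio 1.5.

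| Per arm | Fisher size | Fisher power | Unstratified score power | Stratified CMH power |
|---|---|---|---|---|
| 8 | 0.2% | 9% | 22–24% | 17–21% |
| 16 | 1.5% | 26% | 39–44% | 39–42% |
| 24 | 2.5% | 47% | 58% | 56–58% |
| 40 | 2.6% | 73% | 79–80% | 79–81% |
| 56 | 2.6% | 88% | 91–92% | 91–92% |
| 64 | 2.8% | 92% | 94–95% | 94–95% |

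In the unstratified column, the range at 8 and 16 per arm reflects whether the variance uses N − 1 or N. In the CMH column, the ranges cover unbalanced and balanced strata.

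Fisher's loss is about 3 to 15 points for mid-sized levels. For example, it is 58 − 47 = 11 at 24 per arm and 80 − 73 = 7 at 40. At 16 per arm it is 13 to 18, depending on the form of score test. At 72 per arm it is only 1 to 2 points.

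**Step 3: what causes that loss.** The unstratified score test uses neither CRP nor region, yet it recovers almost all of it. Across the assumed settings, stratifying on top changes power by about −7 to +3 points, and at 8 per arm with unbalanced strata it costs 4 to 5.

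**Step 4: the interaction test, where the covariates matter.** Wald test at 0.10, two equal levels, one regimen against placebo, treatment odds ratios 2 and 10:

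| CRP / region odds ratio | Power without → with both terms | Size without → with both terms |
|---|---|---|
| 2 / 1.5 | 58% → 60% | 9.9% → 10.1% |
| 4 / 2 | 56% → 62% | 8.7% → 8.9% |

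Where neither factor is prognostic the gain is essentially nil. The range is therefore about 0 to 6 points, with size unchanged.

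**The case against.** - **The departure is allowed.** The default has a proviso, and both subgroup sections specify their own model. This stands: it is a prespecified choice, and a reader who infers a contradiction goes too far.
- **Dropping CRP and region does not weaken the within-level tests.** A reader might put the 3 to 15 points down to the missing covariates. Step 3 shows otherwise.
- **Chance CRP imbalance does not pass for heterogeneity at an inflated rate.** A reader might infer this because most subgroup factors are not randomisation strata. Under a homogeneous effect the planned test rejects 8.7% to 9.9% of the time at a nominal 10%, so the inference fails.
- **A like-for-like overall result will exist.** Fisher with nonresponder imputation on the ITT population is already a planned analysis of ASAS40, so subgroup p-values can be read against it. The formal test of consistency is the interaction test, which does not use Fisher.
- **Conservatism has some merit here.** SAP 6.14.1 lists 32 subgroup variables. With three endpoints and two regimens that is 32 × 3 × 2 = 192 analyses, each with two or more levels before the 10% rule, and no multiplicity adjustment. Replacing Fisher outright would roughly double the per-test false-positive rate. This stands against wholesale replacement by a four-stratum CMH test, which would also need a small-sample rule.

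None of this argues against putting the two factors into the interaction model.

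**Conclusion.** This is a free improvement and not a flaw in validity. The subgroup interaction models omit two factors that are already collected and already in the primary model. Including them gains about 0 to 6 points of interaction power and leaves the 10% level intact. The gain depends on prognostic strength, which the documents do not quantify.

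The within-level Fisher test is a separate matter. It is valid, runs at about 1.5% to 3% for levels of 16 to 64 per arm and about 0.2% at the 8-per-arm floor, and gives up about 3 to 15 points in mid-sized levels. A level of 24 per arm with the full assumed effect would be non-significant 100 − 47 = 53% of the time under Fisher, against 100 − 58 = 42% under a score test. A non-significant level should therefore not be read as absence of effect. These figures assume a 5% within-level threshold, which neither subgroup section states.

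The primary and major secondary conclusions are not touched, because subgroups lie outside the multiplicity-controlled family.

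**What to change.** 1. In Protocol 9.7.2 and SAP 6.14.1, add geographic region and baseline CRP status to the subgroup interaction models. Leave out CRP status when the subgroup is a CRP cut (3, 5, 10 or 15 mg/L). Leave out region when the subgroup is country or any of the regional groupings.
2. Within each level, report the treatment difference from the region- and CRP-adjusted logistic model of the primary analysis, with the same omissions, alongside Fisher's test. Report Fisher alone where the model is too sparse to fit, as SAP 6.1.1 already provides.

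The cost is some wording and slightly more programming, with no new data. SAP Section 3 records that Version 3 was approved after unblinding, so results added now must be labelled post hoc and the prespecified results kept beside them.
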